#### **4.5 Follow-up**

All trial patients will be ONS flagged for mortality. HRQL data will be collected at 1, 3 and 12 months following treatment for those allocated to an operation. However, for patients randomised to best medical treatment in EVAR Trial 2 we have incorporated a 1 month delay for the early follow-up in these patients. This takes into account the estimated 1 month delay patients will experience waiting for their EVAR procedure in the EVAR arm of trial 2.

Cost evaluation will be based on operation costs and in patient admissions during the course of follow up. The incidence of any adverse events will also be collected at every follow-up appointment, eg. tender AAA, ruptured AAA, conversion to open repair, myocardial infarction, stroke, renal failure and amputation. CT scan will be used for assessment of growth rates, persistent endoleaks and durability which could vary with stent graft type. CT scan follow-up will be at 1 and 3 months, 1 year, 2 years, 3 years and 4 years for EVAR patients in trial 1 or 2. CT scan follow up will be performed annually for patients randomised to EVAR Trial 1 OR. CT scan follow up will be annually for best medical treatment patients in EVAR Trial 2. Creatinine will be recorded annually for all patients to assess any changes in renal function between the randomised groups.

[figure not shown]
Figure 8 illustrates the treatment procedure for each patient.

*Figure 8 – Patient treatment procedure within EVAR Trials*

### 5. Project Milestones of the program grant

Operator learning curves are completed for 13 centres. The RETA registry has recommended that these centres should form the initial regional trial participants. The 13 co-ordinators have been trained at Charing Cross trial centre in London. Patients will be recruited to both EVAR trials for the whole of the four year period. Follow-up commences from discharge of the first patients and exceed three years for the early patients entered. Evaluation and appraisal of data will be undertaken during the fourth year during which there would need to be close liaison with the DMEC. This committee would play a vital role in both trials. In Trial 1 the monitoring committee will determine and track mortality in OR v EVAR and be in a position to predict if a result is likely and if so when. During the period of this investigation safety, efficacy and durability of EVAR in that trial will be established. If there is any possible chance of showing a difference in mortality in favour of EVAR, EVAR would potentially be the most cost effective method of treating AAA within the NHS. Much shorter hospital stays and reduced pain from absence of the large abdominal incision would be clear advantages.

In Trial 2 the monitoring committee review the mortality closely in the two arms and apply stopping rules if EVAR is clearly showing no adjuvant benefit beyond best medical treatment. If EVAR was abandoned for unfit for OR patients this would constitute great savings to the NHS. If the trial is not performed, we believe that there will be operator pressure for the NHS to provide EVAR in these patients, as these are the type of patients first treated successfully by EVAR. The NHS has funded EVAR Trials 1 and 2 with the intention that NHS money for EVAR procedures will only be available within these trials until an answer is known.

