We are extremely grateful to [name] for suggestions, particularly with respect to building in stopping rules, during trial monitoring. She suggested we take the control group mortality as 25% per annum and assume the expected between group relative difference of around 45% (absolute difference of around 20%) using a 2 tail test to allow for both a possible benefit or possible adverse effect of EVAR. At 90% power and 1% alpha we need around 734 patient years. Alpha is increased to take account informally of 3 looks which would overall give a lower alpha. This can be achieved by randomising 300 patients over 4 years and assuming an average follow-up per patient of 2.5 years with a further minimum one year follow-up to achieve the required number of patient years. If we randomise more patients earlier then we will accrue more patient years more quickly. Then assuming an overall death rate of 30% in the 2 groups if EVAR is worse by 20% or if EVAR is better we will have between 150 to 225 deaths. We could then plan 3 looks based on 75 deaths with stopping rules built in. However if the mortality is lower because EVAR is better we will not get this number of deaths. It would be "safer" to recruit more patients from the outset. If we could recruit 440 patients over the 4 years then we could accumulate 1,000 patient

Sample size calculations are calculated to provide 90% power at the 5% significance level.

	Open repair [UK Aneurysm Trial]	EVAR [Original grant application]	EVAR [RETA 1996 data]	EVAR [RETA 1997 data]	EVAR [RETA 1998 data]
Number dead at 30days Total operated	$\frac{11}{191}$	$\frac{6}{91}$	$\frac{8}{96}$	$\frac{4}{126}$	$\frac{2}{180}$
30 day operative mortality	5.76 %	6.6 %	8.3 %	3.2 %	1.1 %
Numbers required per group (total recruitment) to detect difference between EVAR and OR		17,504 (35,008)	2,205 (4,410)	1,448 (1,896)	361 (722)

In favour of OR

In favour of EVAR

Figure 7 – Numbers of patients required for EVAR Trial 1 to detect a difference in 30 day operative mortality between Open Repair (OR) at 5.76% and EVAR mortality figures according to year of RETA audit.

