The portfolio of instruments to measure HRQL in the proposed trials is designed to be comprehensive yet brief. It will be completed by patients in the form of a questionnaire - at recruitment and subsequently one, three and 12 months after surgery or the beginning of medical treatment as appropriate. The questionnaire will include two generic instruments - the Short-Form 36-item (SF-36) Health Survey and the EuroQol. The SF-36 is a health profile comprising eight distinct scales including physical and social functioning, role limitation, mental health, vitality, pain and general health. It has been shown to be valid, reliable and responsive to changes in health in British patients. The EuroQol is a validated utility measure comprising five items covering mobility, self care, usual activities, pain, anxiety and depression. The HRQL states defined by the various combinations of responses to these items have been valued by the general public for use in cost-utility analysis. Unfortunately we know of no specific instrument designed to measure HRQL in patients suffering from AAA; this has been confirmed by a recent systematic search of Medline. One likely reason for this lack is the wide range of effects that this condition has on patients. In these circumstances we propose to use the State Trait Anxiety Inventory (STAI) which encompasses both the state form (transitory feelings of fear or worry) and the trait form (the stable tendency to respond anxiously to stressful situations or proneness). The STAI measures in-built tendency to anxious response and current feelings of anxiety. It enables the investigator to distinguish between the transitory (state) and the dispositional types of anxiety.

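### Section 5 recruits throughout the four years, evaluates the data in year 4 and gives no later data cut, which conflicts with the further year of follow-up that section 4.1 needs for Trial 2

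*Protocol*

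**What the plan says.** Protocol section 5 (Project Milestones) states "Patients will be recruited to both EVAR trials for the whole of the four year period" and "Evaluation and appraisal of data will be undertaken during the fourth year". On follow-up it says only "Follow-up commences from discharge of the first patients and exceed three years for the early patients entered". It names no stage after the fourth year, yet expects the safety, efficacy and durability of EVAR in Trial 1 to be settled within the investigation.

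Protocol section 4.1 (Mortality, EVAR Trial 2) sets the target: "At 90% power and 1% alpha we need around 734 patient years". The target is to be met with 300 patients entered over 4 years and a mean follow-up of 2.5 years each, on one further condition that the section attaches to this plan: "with a further minimum one year follow-up to achieve the required number of patient years". The same section expects 150 to 225 deaths and suggests three looks, based on 75 deaths.

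Section 4.3 collects HRQL at "one, three and 12 months after surgery or the beginning of medical treatment". Section 4.5 schedules CT at 1 and 3 months and then at "1 year, 2 years, 3 years and 4 years for EVAR patients in trial 1 or 2".

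**The concern.** The sample size for Trial 2 depends on a follow-up year after recruitment closes, and the milestones contain no such year. If section 5 governs the data cut, Trial 2 is analysed on less exposure and fewer deaths than its power statement requires. That matters because section 5 contemplates abandoning EVAR in unfit patients if no benefit is seen, and an underpowered null result could be read that way. The same cut would leave late recruits without the 12-month EuroQol that feeds the cost-utility analysis, and would leave the later CT scans unobserved although durability is a stated aim.

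**Working it through.** **Inputs from the protocol.** Trial 2: 300 patients over 4 years, control mortality 25% a year, relative difference about 45%, two-tailed test, 1% alpha, 90% power (section 4.1). Trial 1: 800 patients over 4 years (Summary). Wait for EVAR in Trial 2: about 1 month (section 4.5).

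**Assumptions.** Even entry over the 4 years, equal arms, constant death rates. The protocol's yearly figures (about 70 and 200 patients, section 3.7) suggest a steady rate but do not fix one.

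**1. Reproducing 734.** Treat each patient-year as one unit and compare p1 = 0.25 with p2 = 0.25 × 0.55 = 0.1375. With pooled p = 0.19375:

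n per arm = [2.576 × √(2 × 0.19375 × 0.80625) + 1.282 × √(0.25 × 0.75 + 0.1375 × 0.8625)]² / 0.1125² = 365, so 730 in total. This is within 1% of the stated 734. The plan's 300 × 2.5 = 750 covers it.

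**2. Exposure if nobody died.** Mean potential follow-up is 4/2 = 2.0 years at the end of year 4, so 300 × 2.0 = 600 patient-years, 18% below 734. A mean of 2.5 years cannot be reached by then with even entry. With one further year the mean is 3.0 years, or 900 patient-years.

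**3. Exposure with deaths.** For death rate λ and F further years after recruitment, mean time at risk is (1/λ) × [1 − (e^(−λF) − e^(−λ(4+F)))/(4λ)].

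At F = 0 this gives 1.472 years (λ = 0.25), 1.679 (λ = 0.1375) and 1.302 (λ = 0.25 × 1.45 = 0.3625).

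- EVAR 45% better: 150 × (1.472 + 1.679) = 473 patient-years; deaths 150 × (1.472 × 0.25 + 1.679 × 0.1375) = 90.
- EVAR 45% worse: 150 × (1.472 + 1.302) = 416 patient-years; deaths 150 × (1.472 × 0.25 + 1.302 × 0.3625) = 126.

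Either way only the first look, at 75 deaths, is reached; the second would need 150.

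At F = 1 the times are 2.031 and 2.397 years (EVAR better): 150 × 4.428 = 664 patient-years and 126 deaths, still short of 734.

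**4. Power for the 45% reduction, two-sided 1% alpha.**

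| Data cut | Patient-years | Formula of step 1 | Log-rank |
|---|---|---|---|
| Plan's target | 734 | 90% | – |
| End of year 4, no deaths | 600 | 82% | – |
| End of year 4, with deaths | 473 | 70% | 60% |
| End of year 5, with deaths | 664 | 86% | 78% |

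Log-rank power is Φ(√D/2 × |ln 0.55| − 2.576), with D = 90 and 126 deaths.

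**5. HRQL and CT at the end of year 4.** Patients randomised in the last 12 months are 12/48 = 25%: 200 of 800 and 75 of 300. With the 1-month wait in Trial 2 the share is 13/48 = 27%, about 81 of 300. A 3-year CT is reachable for at most 12/48 = 25%, and a 4-year CT for essentially nobody.

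**The case against.** The strongest reply is that the year-4 evaluation is not the final analysis. Section 5 never calls it final, ties it to liaison with the DMEC, and asks that committee to predict whether and when a result will come. Section 4.1 makes the timing of looks depend on deaths and patient-years, and sections 3.7 and 4.5 cost and schedule CT to 4 years, which implies follow-up beyond recruitment. This reading is possible, so one cannot say that the protocol has fixed a final cut at year 4. But then section 5 gives no final cut at all, while still promising a durability answer within the investigation. Either reading calls for a correction.

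Faster early recruitment would also narrow the gap, as section 4.1 notes. That stands, but section 4.1 asks for the further year all the same.

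Three stronger inferences are not supported:

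- A reader might set 60% power against the claimed 90%. These come from different methods. By log-rank even a year-5 cut gives about 78%, so the timetable explains only 78% to 60%. The like-for-like fall is 90% to between 70% and 82%.
- A reader might take the mention of discharge in section 5 as each patient's time origin, leaving out in-hospital deaths. The sentence speaks of discharge of the first patients and marks when follow-up activity begins. Section 4.5 has every trial patient flagged with ONS for mortality, and section 4.1 bases Trial 1 on 30-day mortality.
- A reader might apply the 1-month wait to Trial 1. Section 4.5 gives it only for the EVAR arm of Trial 2.

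**Conclusion.** The point holds as a conflict between two sections: section 4.1 depends on at least one year of follow-up after recruitment, and section 5 makes no provision for it. The size is conditional on a cut at the end of year 4 and on even entry. On those terms Trial 2 has at most 600 patient-years, and realistically about 470 (about 420 if EVAR is 45% worse), against 734. A cut earlier in year 4 would lose more. The HRQL loss affects both trials, but it is set by entry date and the protocol states no HRQL sample size that it would breach. Trial 1's mortality comparison needs 722 patients followed for 30 days, with 800 planned, so it is barely touched.

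**What to change.** Amend section 5 to label the year-4 evaluation as interim and to state a final data cut at least 12 months, plus any treatment wait, after the last randomisation, as section 4.1 already assumes. For Trial 2, also tie the cut to reaching 734 patient-years: with even entry, one further year gives only about 660 once deaths are counted, so a calendar date alone would still fall short.

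If year 4 must stand as the final cut, restate Trial 2 as about 420 to 470 patient-years, with about 70% power for the 45% reduction on the protocol's own formula (at the upper end of that range), and limit durability claims to the follow-up actually observed.

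The cost is a final analysis about a year later, somewhat more for Trial 2 if patient-years accrue slowly. ONS flagging and the HRQL forms are already planned. A year-5 cut would complete the 12-month HRQL window, but most patients would still not have reached the 4-year CT, so durability statements need that limit in either case.

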## **6. Methods for Disseminating and Implementing Research Results**

Results will be presented to the Cochrane Research Group for Vascular Disease in Edinburgh and the NHS Centre for Review and Dissemination in York. We would certainly follow the guidelines of the Research and Development Directorate for reporting research results in the NHS. Results would be presented to National and International peer reviewed journals and offered for presentation at national and international societies. In this regard the applicants are well placed within key societies and various discipline groups in the UK and Europe.

